## **VII. Character of Study Variables**

As a routine evaluation of the data during analysis, consistency of the study variables to properties of statistical tests will be done. For continuous variables, equality of variance tests will be done to support analyses requiring this condition such as the Wilcoxon rank sum test. With categorical data, exact statistical test procedures will be used to minimize test assumptions. For tabulated continuous variables, the descriptive analyses will present the mean, standard deviation, median, minimum and maximum. For tabulated categorical variables, the number with the characteristic, the total number evaluated, the percent and the 95% exact binomial confidence intervals will be provided.

## **VIII. Comparability Analyses of the Patient Populations**

Baseline characteristics for the subjects in the validation study will be presented descriptively. Quantitative variables will have the mean, standard deviation (SD), number evaluated, median, minimum and maximum presented. Qualitative variables will have the number with the characteristic, the number evaluated, the percentage, and the exact 95% confidence limits on the percentage presented.

In addition, an analysis of comparability across study sites will be carried out. For continuous variables, this will be done by parametric or non-parametric analysis of variance. For categorical variables, the Fisher-Freeman-Halton test will be used. Study site differences do not disallow pooling, but variables including study site and the variable found different need to be considered as covariates in subsequent multivariate analyses.

Because some study sites will have too few subjects to permit an adequate evaluation, it will be necessary to combine study sites with less than 8 subjects together to form pseudo-sites that will have adequate numbers of subjects to support analyses by pseudo-site. The combination will be done in an unbiased manner without regard to study results. The study site with the lowest site number with fewer than 8 subjects will be combined with the next site in numerical order with fewer than 8 subjects. This process will be continued until the pseudo-site formed has 8 or more subjects. Study sites with 8 or more subjects will be assigned a pseudo-site number to allow analysis. No pseudo-site created by this process will have a greater number of subjects than the median of the sites that have 8 or more subjects. Pseudo-sites will also be used for the site comparability analyses and the data pooling analysis below.

## **IX. Patient Accountability and Missing Data**

A summary table will provide the total number of subjects enrolled and completed. Subjects withdrawn will be tabulated with their reasons for withdrawal and subjects missing either a diagnosis result or ProLung Test result will be tabulated with which of the two evaluations is missing.

Every effort will be made to collect all data points in the study. The sponsor plans to minimize the amount of missing data by appropriate management of the prospective clinical trial, proper screening of study subjects, and training of participating investigators, monitors and study coordinators. The sponsor will provide a list of subjects who do not complete the trial along with the best information available on why each had missing data.

The number of subjects with missing data is expected to be a small proportion of total subjects in the study. If the diagnosis result is missing it is not possible from subject characteristics to estimate or impute a result for any given subject. Likewise, if the ProLung Test result is missing it is not possible to determine from baseline subject characteristics to estimate or impute the missing result of the test. Thus, these subjects will not be used in the analysis. A descriptive comparison of the baseline characteristics of the ITT and CC subjects will be presented to demonstrate that there is little bias from the missing data.

A sensitivity analysis will be done for cases with missing data that assigns cases with missing results the worst-case scenario, i.e. that the ProLung result is negative if cancer is detected or that the ProLung result is positive when cancer is not detected. A second analysis will be done as a best-case scenario, i.e., the ProLung result will be deemed positive when cancer is present and will be deemed negative when cancer is not detected.

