3.4 Study Sample Size

This Study may enroll a maximum of 200 in the Stabilization Phase and 150 in the Validation Phase. The Study may enroll a minimum of 100 in the Stabilization Phase and 100 in the Validation Phase. In the Validation Phase, the sample size has been determined to provide greater than 90% power to reject the primary study hypothesis.

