With respect to determining the optimal sample size of the Validation Phase, it is assumed that the sensitivity of the ProLung test (probability of having had a high risk test among subjects who subsequently had a malignant biopsy) is 70% and that the specificity (probability of having had a low risk test among subjects who subsequently had a benign biopsy) is also 70%. It is further assumed that among the patient population studied in this Study, approximately 70% will have a malignant biopsy. Based on these assumptions, 88 subjects will provide 90% power to reject the primary null hypothesis. The primary analysis will only include subjects who have a biopsy within 60 days of their ProLung test and have a definitive biopsy result. Subjects who fail to have a biopsy or do not have a definitive biopsy result will be excluded. To account for as many as 12% of such subjects, 100 subjects will be enrolled into the Validation Phase. Furthermore, to maintain the Study's statistical power, enrollment will continue until there is both a minimum of 100 subjects and a minimum of 40 ProLung high risk and a minimum of 40 ProLung low risk subjects are enrolled.

The primary null hypothesis is that the relative risk of a malignant biopsy among subjects with a high risk ProLung test result to that of subjects with a low risk ProLung test result is 1.0, vs. the alternative hypothesis that the relative risk is different from 1.0. This hypothesis will be tested by a two-sided Fisher's Exact Test at the 5% level of significance. If the relative risk is found to be greater than 1.0

($p < 0.05$), it will be concluded that subjects with a high risk ProLung test result are prognostically at greater risk to have a malignant biopsy than subjects with a low risk ProLung Test result. The relative risk will also be presented with its approximate 95% confidence interval.

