## **Analysis Summary**

**Study Title:** A Multi-Center Trial of the ProLung Test (Transthoracic Bioconductance Measurement) as an Adjunct to CT Chest Scans for the Risk Stratification of Patients with Pulmonary Lesions Suspicious for Lung Cancer (Protocol PL-208)

**Primary Objective:** To demonstrate that the ProLung Test can assist in the assessment of patients presenting with indeterminant CT scans.

**Primary Endpoint:** The coprimary endpoints are the Positive Predictive Value (PPV) and Negative Predictive Value (NPV)

**Secondary Endpoints:** Co-secondary endpoints of sensitivity and specificity of the ProLung Test and the sum of PPV and NPV

**Additional Endpoints:** Additional Effectiveness Endpoint Analyses - Subgroup Analyses of NPV, PPV, sensitivity and specificity.

**Patient Population:** Males and females aged 18 years and older with a CT scan of the lungs that indicates one or more nodules or lesions suspicious for lung cancer.

**Study Design:** A single arm multicenter study of subjects with CT scans with nodules of undetermined significance and known diagnosis to be used to validate the ProLung Test to stratify the positive risk of lung cancer.

**Number of Patients:** 174 subjects with paired ProLung test result and a biopsy or radiological stability diagnosis for lung cancer.

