## **IV. Analysis Populations**

### **A. Intent-to-Treat (ITT) Population**

The intent-to-treat population is every subject that is enrolled in the study.

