### **B. Completed Cases (CC) Population**

All subjects that have paired results of both ProLung Test and either confirmatory tissue biopsy (of cancer or benign condition) or radiologic stability to infer a benign diagnosis.. The primary and secondary analyses require paired evaluations and therefore will be conducted in the completed cases population.

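### The planned baseline check for missing-data bias compares completed cases with an ITT set that contains them, which obscures whether the excluded subjects differ

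*SAP*

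**What the plan says.** SAP section IV defines two sets. For ITT: "The intent-to-treat population is every subject that is enrolled in the study". For CC it begins: "All subjects that have paired results of both ProLung Test and either confirmatory tissue biopsy", and it also accepts radiologic stability as a benign diagnosis. The primary and secondary analyses use CC.

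SAP section IX does not impute a missing diagnosis or a missing ProLung result; those subjects leave the analysis. On how many there will be, it says only: "The number of subjects with missing data is expected to be a small proportion of total subjects in the study". The baseline check is then described: "A descriptive comparison of the baseline characteristics of the ITT and CC subjects will be presented to demonstrate that there is little bias".

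The same section plans a tabulation of withdrawals by reason, a tabulation of which evaluation is missing, a list of non-completers with the best available explanation, and worst-case and best-case analyses. No table sets CC subjects against the subjects left out.

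The only numerical loss rate is in Protocol section 8.1: "To account for as many as 12% of such subjects, 100 subjects will be enrolled into the Validation Phase". It belongs to an analysis restricted to subjects with a definitive biopsy within 60 days of the ProLung test.

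**The concern.** Two columns that share most of their subjects will resemble each other whatever the remaining subjects are like. The fewer the exclusions, the closer the resemblance, and the SAP expects few. The purpose clause also states the conclusion before any data are seen.

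This matters because loss need not be random. Protocol section 4.3.2 removes subjects for inconclusive biopsy, lost records or incomplete ProLung data. Section 4.3.1 lists a missed one-year follow-up CT as a possible ground for discontinuation. SAP section XII excludes scans for quality problems, including an open-ended category. The co-primary endpoints are PPV and NPV, which the SAP itself adjusts for prevalence in section V.A.1. Loss related to disease status or patient type could therefore move both endpoints. A reader wanting to know whether the lost subjects were unusual would look to this table, which presents that information in its least visible form.

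**Working it through.** **Inputs**
- CC lies within ITT (SAP sections IV.A and IV.B).
- Loss allowance: up to 12% (Protocol section 8.1).
- Evaluable number in the protocol: "Based on these assumptions, 88 subjects will provide 90% power to reject the primary null hypothesis".
- CC size in the SAP's Analysis Summary: "174 subjects with paired ProLung test result and a biopsy or radiological stability diagnosis for lung cancer".
- Enrolment limits in Protocol section 3.4: "This Study may enroll a maximum of 200 in the Stabilization Phase and 150 in the Validation Phase". Section 3.2 allows up to 35 replacements across the two phases.
- Assumed for illustration, not taken from the documents: an 8-year age gap and a 30-point gap in a proportion between CC and excluded subjects.

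**The protocol's own figure.** 88 / (1 − 0.12) = 100, which matches the planned enrolment.

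**Identity.** Let f = (N_ITT − N_CC) / N_ITT. Then

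mean(ITT) = (1 − f) × mean(CC) + f × mean(excluded),

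so mean(CC) − mean(ITT) = f × [mean(CC) − mean(excluded)].

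The displayed difference is the CC-versus-excluded difference divided by 1/f. The same holds for proportions.

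**Numbers**

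| Assumption | f | 1/f | 8-year gap shows as | 30-point gap shows as |
|---|---|---|---|---|
| 20% excluded | 0.20 | 5 | 1.6 years | 6.0 points |
| 12% (protocol allowance) | 0.12 | 8.3 | 0.96 years | 3.6 points |
| 10% excluded | 0.10 | 10 | 0.8 years | 3.0 points |
| 174 of 185 complete | 11/185 = 0.059 | 16.8 | 0.48 years | 1.8 points |
| 5% excluded | 0.05 | 20 | 0.4 years | 1.5 points |

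The 185 row takes the cap of 150 plus all 35 replacements. Carrying 12% over to 174 completers would need 174 / 0.88 ≈ 198 enrolled, hence about 24 excluded. That is more than 185, so 12% is an illustration and not an estimate for this cohort.

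**If ITT covered both phases.** Section IV.A does not limit ITT to the Validation Phase. Adding 200 Stabilization subjects to 198 gives 398, f = (398 − 174) / 398 = 0.56 and 1/f = 1.8. The shrinkage is small, but the comparison would then mainly reflect study phase and not missing data.

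**What a direct comparison can show.** Take 174 CC and 24 excluded subjects, with proportions of 60% and 30%:
- SE = √(0.6 × 0.4 / 174 + 0.3 × 0.7 / 24) = 0.101
- z = 0.30 / 0.101 ≈ 3.0
- 95% interval: 30 ± 1.96 × 10.1, about 10 to 50 points

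The ITT-versus-CC table would show the same situation as a gap of 3.6 points.

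**Limit of splitting by reason.** Three reasons among 24 subjects leave about 8 each. For 8 against 174 near 50%, the half-width is 1.96 × √(0.25/8 + 0.25/174) ≈ 35 points, too wide to be useful.

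**The case against.** The best defence is that CC minus ITT is a meaningful quantity. It is exactly how far the analysed sample's baseline has moved from that of the enrolled sample. If 12% are excluded and they differ by 8 years, the analysed mean has moved by only about 1 year. This stands, and it is why the ITT column should stay. Whether the excluded subjects differ is a second question, and this layout answers it poorly. Neither comparison can rule out loss related to the outcome itself.

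A reader might infer that this table is the SAP's only evidence on missing data. It is not: section IX also plans tabulations of reasons, a list of non-completers, and worst-case and best-case analyses. Those analyses address the effect on the endpoints, which no baseline table can do. Their limits are that the wording assigns only the ProLung result, gives no rule for a missing diagnosis, and does not describe the lost subjects at baseline.

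A reader might also infer that selective loss could not be detected at all. That goes too far. SAP sections VII and VIII call for counts, denominators, percentages and means. If both columns follow that format, the excluded group's counts and means can be recovered by subtraction. Medians cannot, nor can a breakdown by reason, and a planned check should not depend on readers doing this.

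**Conclusion.** The point holds as a weakness in one descriptive table. The comparison is nested, so a difference between completed and excluded subjects appears multiplied by f. That is an identity and needs no assumption.

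The size does need one. An eight-fold shrinkage might be read as a property of this study, but the documents do not support that. It is 1/0.12, from an upper allowance set for a biopsy-only analysis of 100 subjects, whereas the SAP's CC set also accepts radiologic stability and numbers 174. A range of about 5-fold (20% excluded) to 20-fold (5%) is the fair statement.

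Nor do the documents show that the results will be biased, or that little bias will be claimed regardless of the data; the table is descriptive and has no decision rule. The primary analysis is unaffected. This is a low-severity improvement, worth making because it is nearly free.

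**What to change.** In SAP section IX:

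1. Keep the ITT and CC columns and add one for enrolled Validation Phase subjects excluded from CC.
2. Show the CC-minus-excluded difference with its 95% interval for the excluded group as a whole. Give any breakdown by reason (no diagnosis, no ProLung result, scan excluded for quality) as counts or descriptively only, since the cells will be small.
3. Replace the purpose clause with wording such as 'to assess potential bias'.
4. State that ITT in this comparison means Validation Phase enrolees.

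The cost is one table column, one difference column and two wording changes. Protocol sections 5.1 and 5.4 already collect the baseline data at the patient visit, so nothing new is asked of sites or subjects.

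### The worst-case and best-case rule in SAP Section IX has no instruction for a subject with a ProLung result but no diagnosis, so it does not bound the effect of missing diagnoses

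*SAP*

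**What the plan says.** SAP Section IX provides that "subjects missing either a diagnosis result or ProLung Test result will be tabulated with which of the two evaluations is missing", so both kinds of missing data are foreseen. For the main analysis neither is imputed. On the diagnosis it says: "If the diagnosis result is missing it is not possible from subject characteristics to estimate or impute a result for any given subject". It says the same of a missing ProLung result, and both kinds of subject are left out. SAP Section IV.B accordingly runs the primary and secondary analyses on completed cases only.

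The section then turns to bounding. Its lead-in is general and covers cases with missing data of either kind. The rule that follows is specific. It "assigns cases with missing results the worst-case scenario, i.e. that the ProLung result is negative if cancer is detected", or positive when it is not; in the best case, "the ProLung result will be deemed positive when cancer is present and will be deemed negative when cancer is not detected". Both sentences set the ProLung result according to the diagnosis. Neither sets a diagnosis.

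The protocol shows that missing diagnoses can occur. Section 4.3.2 removes inconclusive biopsies from the primary analyses, and Section 4.3.1 lists a missed follow-up CT (one year plus 60 days) as a possible reason for discontinuation.

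**The concern.** The lead-in promises a bound for all missing data, but the rule can be carried out for only one kind. A subject with an observed ProLung result and no diagnosis has nothing to be assigned. Stretching the no-cancer-detected clause to cover an absent diagnosis does not help: it would overwrite an observed test result, and it could never produce a false negative.

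Missing diagnoses matter here because whether one is obtained depends on biopsy yield and on follow-up, both of which may be related to the lesion. The descriptive baseline comparison of the ITT and completed-case populations does not bound an outcome. The report could therefore say that the result survives the worst case when an adverse reading of the missing diagnoses would lose a co-primary goal. SAP Section VI requires both co-primaries to succeed, so one loss is enough.

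**Working it through.** **Inputs.** SAP V.A.1 gives expected counts of 78 TP, 22 FP, 41 TN and 33 FN, and goals of 0.638 (PPV) and 0.381 (NPV). SAP X.A gives an exact one-sided binomial test at 0.025, or equivalently the lower 97.5% limit. The SAP Analysis Summary gives 174 completed cases. Protocol 3.4 gives a Validation Phase maximum of 150, and Protocol 3.2 up to 35 replacements across the two phases.

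**Reproducing the plan's figures.** PPV = 78/(78+22) = 0.780 against the stated 0.778. NPV = 41/(41+33) = 0.554 against the stated 0.551 to 0.552. The differences come from rounding to whole subjects. The exact (Clopper-Pearson) lower limits are 0.686 and 0.434, with p = 0.0016 and 0.0019, so both goals are met.

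**The existing rule, for a missing ProLung result.** One cancer case set to negative leaves PPV at 78/100 and lowers NPV to 41/75 = 0.547. One benign case set to positive lowers PPV to 78/101 = 0.772 and leaves NPV at 41/74. Both moves are adverse, so for this kind of missing data the rule is the true worst case.

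**The existing rule, for a missing diagnosis.** It assigns nothing. PPV stays at 78/100 and NPV at 41/74 for any number of such subjects.

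**Counting missing diagnoses adversely.** A test-positive subject becomes FP and a test-negative subject becomes FN. With a test-positive and b test-negative subjects, PPV = 78/(100+a) and NPV = 41/(74+b).

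| Added subjects | Ratio | Lower 97.5% limit | Exact p | Goal met? |
|---|---|---|---|---|
| a = 6 | 78/106 = 0.736 | 0.641 | 0.021 | PPV yes |
| a = 7 | 78/107 = 0.729 | 0.634 | 0.030 | PPV no |
| b = 9 | 41/83 = 0.494 | 0.382 | 0.024 | NPV yes |
| b = 10 | 41/84 = 0.488 | 0.377 | 0.029 | NPV no |

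**How many could be missing.** The documents do not give final validation enrolment. The protocol ceiling is 150 + 35 = 185 if every replacement goes to validation, which leaves 185 − 174 = 11 subjects (11/185 = 5.9%) without paired results for any reason. In the SAP's 100:74 ratio of test results, 11 × 100/174 = 6.3, so about 6 test-positive and 5 test-negative. That gives 78/106 (limit 0.641) and 41/79 = 0.519 (limit 0.404), and both goals are met. If 7 or more of the 11 were test-positive, the PPV goal would be lost.

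**The case against.** **Exclusion is inferred, not stated.** A reader might infer that the SAP decided to leave missing diagnoses out of the bounding analyses. It does not say so, and its lead-in covers all cases with missing data. What stands is that the rule is incomplete for this kind of missing data.

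**The 12% allowance.** A reader might also infer that both goals fail at the protocol's own planning rate, since Protocol 8.1 says "To account for as many as 12% of such subjects, 100 subjects will be enrolled" (88/0.88 = 100). Applied to 174, that gives 174/0.88 ≈ 198 enrolled and 24 missing, split 14:10. The limits would be 0.590 for 78/114 and 0.377 for 41/84, both below goal. The documents do not support using this as the headline, for two reasons. First, 198 exceeds the ceiling of 185. Second, the 12% belongs to a primary analysis restricted to subjects with a definitive biopsy within 60 days. The SAP also accepts radiological stability, and Protocol 3.0 classes a nodule with no growth and no definitive biopsy as benign unless the record says otherwise, so some of those subjects would have a diagnosis under the SAP.

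**Few may be missing.** The SAP expects only a small proportion, and on the expected counts 11 subjects split 6:5 leave both goals met. This stands, and it limits the size of the problem.

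**There are partial safeguards.** The SAP tabulates which evaluation is missing and lists the reasons. Protocol 5.10 re-confirms benign and stable outcomes before study close, and Protocol 3.2 allows replacement of subjects lost to follow-up. These let a reader count the exposure but do not bound it.

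**It is a supplementary analysis.** Neither the primary test nor the multiplicity rule depends on it. This stands too, and it keeps the point at the level of a recommended correction.

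**Conclusion.** The point holds as a gap in the rule. SAP Section IX bounds missing ProLung results correctly and does not bound missing diagnoses, in the worst case or the best case. On the expected counts the margin is 6 adverse test-positive subjects for PPV and 9 adverse test-negative subjects for NPV; one more of either reverses the co-primary conclusion.

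Whether the conclusion is actually at risk cannot be settled from the documents. It depends on the final count of missing diagnoses and how they divide by test result, and neither is given. The tipping points assume that the observed table matches the SAP's expected counts. The 6:5 split assumes that missing diagnoses follow the 100:74 ratio. The limit of 11 assumes that the protocol's ceiling was kept and that all 35 replacements went to validation; fewer would leave less room. Subjects missing only a ProLung result use the same margin: under the existing rule each benign one adds to the PPV denominator and each malignant one to the NPV denominator.

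**What to change.** Add to SAP Section IX, before test results are linked to diagnoses:

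1. A subject with a ProLung result and no diagnosis is counted in the worst case as FP if test-positive and FN if test-negative. In the best case this is reversed (TP if test-positive, TN if test-negative). Apply this together with the existing rule for missing ProLung results.
2. A subject missing both results is counted as FP for the PPV bound and as FN for the NPV bound (best case: TP and TN respectively). The two bounds then need not come from a single two-by-two table, and the SAP should say so.
3. Report the PPV and NPV lower 97.5% limits against 0.638 and 0.381 under these rules, with the number of missing diagnoses by test result and the number at which each goal is lost.

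The cost is a few sentences and one more table, and the bound will look less favourable. The primary analysis, sample size and study conduct do not change.
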